## CONFIDENTIEL / CONFIDENTIAL

## STATISTICAL ANALYSIS PLAN

- Derived criterion "exclusion of the false lumen without endoleak" will be defined as follows:  
"Exclusion of the main entry of the dissection" will be YES if:
  - no false lumen perfusion type Ia, Ib, III is ticked
  - and "Incorrect Deployment" is not ticked or "false lumen perfusion through a tear proximal to the device in an untreated segment (not an endoleak)" is not ticked
  - and "Status of false lumen located opposite the treated part of the aorta" is "Complete thrombosis"
 If the perfusion status is unknown or if the false lumen thrombosis status is unknown then "exclusion of the false lumen without endoleak" will be missing.
- Derived criterion "exclusion of the penetrating aortic ulcer without endoleak" will be defined as follows:  
No maximum aortic diameter of the ulcer increase > 5 mm (compared to 1st post-op exam) and no type I or type III endoleak
- Derived criterion "exclusion of the rupture site without endoleak" will be defined as follows:  
No type I or type III endoleak
- Mortality from thoracic disease is defined as any death occurring as a result of complication of aortic disease (rupture, conversion, etc.) or following any surgery intended to treat the aortic disease. It will be derived as follows:
  - If the death occurs within 30 days after the initial procedure or any re-intervention or
  - If the death is related to the disease
 Then mortality from thoracic disease will be "YES"
- An adverse event (or any other parameter that is not reported in a follow-up CRF) will be considered as having occurred
  - "at 1 month" if it occurs between the procedure (included) and 30 days after the procedure
  - "at 1 year" if it occurs between the procedure (included) and 365 days after the procedure
  - "at 2 year" if it occurs between the procedure (included) and 731 days after the procedure
  - "at 3 year" if it occurs between the procedure (included) and 1096 days after the procedure
  - "at 4 year" if it occurs between the procedure (included) and 1461 days after the procedure
  - "at 5 year" if it occurs between the procedure (included) and 1826 days after the procedure

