2.2.2 Secondary endpoint criteria

The secondary endpoints assessing the usefulness of the technique at different follow-up visits (after surgery or in the months following the surgery, at 1 year, 2 years, 3 years, 4 years and 5 years) will be:

- The exclusion rate of aneurysm, of penetrating aortic ulcer, of false lumen or site of rupture, with no endoleak, as defined above
- The rate of neurological complications
- The rate of cardiac, renal and pulmonary complications
- The rate of device-related complications
- The rate of surgical conversion
- The rate of secondary procedures
- The rate of mortality related to the disease

Definitions:

- Migration: movement evaluated on a workstation with 3D reconstruction according to the reference examination (1st post-op imaging examination)
 - Proximal movement > 10 mm or ≤ 10 mm with coverage of a branch of the supra-aortic trunks
 - Distal movement > 10 mm or ≤ 10 mm with coverage of the celiac trunk
- Exclusion of the aneurysm:
 - No type I or type III endoleak associated with the lack of increase in the maximum diameter of the aneurysm sac > 5 mm (reference examination 1st post-operative examination)
- Exclusion of the penetrating ulcer:
 - No type I or type III endoleak associated with the lack of increase in the maximum aortic diameter compared to the ulcer > 5 mm (reference examination 1st post-operative examination)
- Exclusion of rupture site:
 - No type I or type III endoleak
- Exclusion of the false lumen (dissection):
 - Exclusion of the main entry of the dissection
 - Thrombosis of the false lumen at the endoprosthesis
- Mortality from thoracic disease is defined as any death occurring as a result of complication of aortic disease (rupture, conversion, etc.) or following any surgery intended to treat the aortic disease.

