### Secondary Analyses

Table 49: Rate of exclusion of aneurysm, false lumen, penetrating aortic ulcer or rupture site, with no type I or III endoleak - by time point (Type 4)

Table 50: Rate of exclusion of aneurysm with no type I or III endoleak - by time point (Type 4)

Table 51: Rate of exclusion of false lumen with no type I or III endoleak - by time point (Type 4)

Table 52: Rate of exclusion of penetrating aortic ulcer with no type I or III endoleak - by time point (Type 4)

Table 53: Rate of exclusion of rupture site, with no type I or III endoleak - by time point (Type 4)

Table 54: Neurological complications rate - by time point (Type 4)

Table 55: Cardiac, renal and pulmonary complications rate - by time point (Type 4)

Table 56: Device-related complications rate - by time point (Type 4)

Table 57: Surgical conversion rate - by time point (Type 4)

Table 58: Secondary procedures rate - by time point (Type 4)

Table 59: Mortality rate related to the disease - by time point (Type 4)

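### The SAP's false-lumen exclusion rule joins two flags with 'or', so read literally neither flag has any effect on its own

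*SAP*

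**What the plan says.** Protocol section 2.2.2 defines exclusion of the false lumen in dissection by two elements: "Exclusion of the main entry of the dissection" and "Thrombosis of the false lumen at the endoprosthesis".

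SAP section 2.5 turns this into a derivation from form items. It sets the main-entry item to YES when three conditions, linked by 'and', all hold:

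1. On endoleak-type perfusion: "no false lumen perfusion type Ia, Ib, III is ticked".
2. On the Incorrect Deployment box, that it "is not ticked or 'false lumen perfusion through a tear proximal to the device in an untreated segment (not an endoleak)' is not ticked".
3. On thrombosis: "and 'Status of false lumen located opposite the treated part of the aorta' is 'Complete thrombosis".

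A closing line says that "If the perfusion status is unknown or if the false lumen thrombosis status is unknown then" the derived criterion is set to missing. No bracket, note or other section gives the 'or' in the second condition a different meaning.

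The result feeds Table 51 (false-lumen exclusion by time point) and the pooled exclusion rate in Table 49. Exclusion is the first secondary endpoint listed in SAP section 2.4.3.2.

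**The concern.** The first condition fails a patient on any one of three perfusion types. The second lists two further adverse findings, but the connector means that neither counts alone. Asking that one box or the other be unticked is an easy misdrafting of asking that neither be ticked, and a programmer following the text will code the literal version.

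The remaining conditions do not fully cover the gap. The thrombosis item describes the false lumen beside the treated part of the aorta, whereas the proximal-tear box describes an untreated segment above the device. Complete thrombosis in the first can coexist with perfusion in the second. The missing-data line does not apply either, because a ticked tear is a known perfusion finding.

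At stake is what a reported false-lumen exclusion means in a named secondary endpoint of a study that reports every year to the French National Health Authority.

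**Working it through.** **Inputs** (all from SAP section 2.5). Four yes/no items:

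- P: type Ia, Ib or III false-lumen perfusion ticked.
- A: Incorrect Deployment ticked.
- B: perfusion through a proximal tear in an untreated segment ticked.
- T: complete thrombosis opposite the treated part.

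I take a YES on the main-entry item to be a YES on the derived criterion, since the thrombosis condition sits in the same list and no other line sets the criterion.

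**Rules compared**

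- As written: YES = (not P) and [(not A) or (not B)] and T. Since (not A) or (not B) is the same as not (A and B), the middle term means 'not both ticked'.
- Alternative: YES = (not P) and [(not A) and (not B)] and T, that is, 'neither ticked'.

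**Enumeration.** Four binary items give 2 × 2 × 2 × 2 = 16 combinations. In 12 of them P is ticked or T is not met, and both rules return NO. The other four, with P unticked and T met, are:

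| A: Incorrect Deployment | B: proximal-tear perfusion | As written | Neither ticked |
|---|---|---|---|
| no | no | YES | YES |
| no | yes | YES | NO |
| yes | no | YES | NO |
| yes | yes | NO | NO |

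The second condition on its own passes in 3 of the 4 (A, B) combinations as written, against 1 of 4 under 'neither ticked'. The full derived result differs in 2 of 16 combinations: A alone and B alone.

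**Direction.** Every patient who is YES under 'neither ticked' is also YES as written. The missing-data line is the same for both rules, so the denominator of non-missing patients does not change. The reported rate as written is therefore equal to or higher than the rate under 'neither ticked', never lower.

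**Size.** The difference in Table 51 at a given time point is

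(patients with A only + patients with B only, among those with P unticked and T met) ÷ (dissection patients with a non-missing result).

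In Table 49 the numerator is the same and the denominator covers all indications, so the effect is diluted. The documents give neither the frequency of A or B nor their overlap with T, so no figure can be put on either difference.

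**The case against.** The strongest reply is that the 'or' may be deliberate. The protocol asks for exclusion of the main entry, not of every entry, and its definition names neither flag. The form label places the tear in an untreated segment and says it is not an endoleak. One coherent reading is that such a tear does not show that the main entry was missed unless the device was also wrongly deployed, which makes joint failure the intended proxy. The thrombosis item is also close to the protocol's own wording, which asks only for thrombosis at the device. And changing to 'and' would make incorrect deployment alone a failure, even with no perfusion and complete thrombosis, which nothing in the protocol definition requires.

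All of this stands as a reason not to declare the rule wrong. A reader might infer that the 'or' is a proven error that overstates exclusion by a material margin. The documents do not support that: they do not state the intent, and they supply no frequencies from which to compute a margin.

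It is also fair to say that the consequences are bounded. This is one component of a descriptive secondary endpoint. The only between-group test the SAP names is the log-rank test for survival analyses, and the text available sets no success threshold for exclusion. By their titles, Tables 34, 42 and 64 and Listings 15 and 20 show false-lumen perfusion separately, and Tables 36 and 37 show deployment inaccuracy. The findings are not hidden. However, none of these titles indicates how many patients counted as excluded carry one of the flags, so they do not settle what the rate in Table 51 means.

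**Conclusion.** The point holds as a defect in a stated rule. Followed literally, the second condition in SAP section 2.5 gives each flag no effect on its own. A patient with documented proximal-tear perfusion, no type Ia, Ib or III perfusion and complete thrombosis beside the device is counted as excluded unless Incorrect Deployment is also ticked. The same applies in reverse to incorrect deployment alone.

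The result differs from a 'neither ticked' rule in 2 of 16 input combinations, and any difference raises the rates in Tables 51 and 49. The size is unknown. If the joint rule is what the sponsor intends, there is no coding error, but the SAP still needs to say so. All-cause mortality, the primary endpoint, is not affected. This should be settled before the tables are programmed.

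**What to change.** State the intended logic explicitly, in one of two ways:

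- If each flag is meant as a failure criterion, replace 'or' with 'and', so that neither box may be ticked.
- If only the joint case is meant as failure, write 'not both ticked' and give the reason. Then show the exclusion rate in Table 51, and in Table 49, a second time with proximal-tear perfusion counted as failure.

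The first option costs one word in the SAP and one line of code. The second costs a clause and an extra row per table, from data already collected. The reported exclusion rate may come out lower. With 'and', patients with incorrect deployment alone also become failures, and the sponsor should confirm that this is intended before adopting it.

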## 2. STATISTICAL METHODS

### 2.1. General Statistical Considerations

#### 2.1.1. Descriptive Statistics in Summary Tables

- Continuous variables will be summarized using standard quantitative statistics: number of non-missing observations, mean, standard deviation, median, quartiles and range (minimum and maximum observed values). The number of missing observations will also be specified.
- Categorical variables will be summarized using classical frequency statistics: number of non-missing observations and percentages by categories. Percentages will be calculated on the number of non-missing observations and will be displayed using one decimal, the corresponding bilateral 95% CI will be presented if appropriate. The number of missing observations will also be specified.

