#### 2.1.3. Handling Missing Data

No replacement of missing data is planned.

If a patient interrupts the study before the end of study, he/she will be considered as missing from his/her last follow-up.

Patients will be considered as censored at the date of the last observation in survival analyses.

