#### 2.4.3.2. Secondary Analyses

The secondary endpoints for assessing the usefulness of the technique will be:

- The exclusion rate of the aneurysm, the false lumen, the penetrating aortic ulcer or rupture site, with no type I or III endoleak (overall and by main indication for implantation)

It will be presented as categorical variables (with the corresponding 95% bilateral CI) by time-point, starting at 30 days.

- The rate of neurological complications
- The rate of cardiac, renal and pulmonary complications
- The rate of device-related complications
- The rate of surgical conversion
- The rate of secondary procedures (re-interventions)
- The rate of mortality related to the disease

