## 2.5. Derived Criteria Calculation

- A patient will be considered as fulfilling the eligibility criteria if:
  - Inclusion criterion 1 is ticked YES
  - Inclusion criterion 2 is ticked YES or date of informed consent is filled
  - Inclusion criterion 3 is ticked YES
  - Exclusion criterion 1 is ticked NO
  - Exclusion criterion 2 is ticked NO
- Total study duration will be calculated as:  
Total study duration = study exit date - procedure date +1  
If the procedure date is not available, the baseline date will be used instead.
- Study follow-up duration will be calculated as:  
Study follow-up duration = last FUP date available - procedure date +1  
If the procedure date is not available, the baseline will be used instead.  
If the visit date is not available, the corresponding last imaging date will be used instead.
- Body Mass Index will be calculated as:  
 $BMI = \text{weight (kg)} / (\text{height (m)})^2$
- Derived criterion “life-threatening emergency” will be derived as follows:
  - if vital urgency specify is “Aortic rupture” then life-threatening emergency will be “Yes: Aortic rupture”
  - else if vital urgency specify is “Dissection complicated by malperfusion” then life-threatening emergency will be “Yes: Dissection complicated by malperfusion”
  - else if vital urgency specify is “Other” then life-threatening emergency will be “Yes: Other”
  - else if vital urgency is “No” then life-threatening emergency will be “No”
- Derived criterion “procedure duration” will be calculated as follows:  
Procedure duration = procedure end time – procedure start time
- Derived criterion “exclusion of the aneurysm without endoleak” will be defined as follows:  
No maximum diameter of the aneurysm sac increase > 5 mm (compared to 1st post-op exam) and no type I or type III endoleak

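### SAP 2.5 sets false-lumen exclusion to missing even when a known component already shows failure, so Table 51's single Missing row can hide documented failures among undetermined patients

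*SAP*

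**What the plan says.** Protocol 2.2.2 defines exclusion of the false lumen by two parts: the main entry is excluded, and the false lumen is thrombosed at the endoprosthesis.

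SAP 2.5 turns this into three conditions joined by 'and': no type Ia, Ib or III perfusion is ticked; the incorrect-deployment box or the proximal-tear box is unticked; and the false lumen opposite the treated aorta is completely thrombosed. It then states that "If the perfusion status is unknown or if the false lumen thrombosis status is unknown then" the false-lumen endpoint is missing. No rule for NO is written, and no exception covers a component that already fails. The conditions carry the label for main-entry exclusion, while the missing clause names the whole endpoint. Since thrombosis is among the conditions, I read both as describing one variable.

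Other relevant provisions:

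- SAP 2.1.1: "Percentages will be calculated on the number of non-missing observations".
- SAP 2.1.3: "No replacement of missing data is planned".
- SAP 2.4.3.2: exclusion is reported "by time-point, starting at 30 days".
- SAP 4.1: Table 51 gives the false-lumen rate, and Table 49 pools it with the aneurysm, ulcer and rupture-site criteria.
- SAP 5.2.2: the Type 4 layout used for both tables has one undivided Missing row.

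The aneurysm criterion ("No maximum diameter of the aneurysm sac increase > 5 mm") and the ulcer criterion ("No maximum aortic diameter of the ulcer increase > 5 mm") each also require no type I or III endoleak. Neither has a clause on unknown components.

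**The concern.** When success needs every condition, one known failure settles the answer whatever the other components show. The missing clause overrides that. A patient with documented type Ia perfusion and unreadable thrombosis cannot be a success under the SAP's own definition, yet is filed with patients whose status really is open.

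What is at stake is how far Table 51 can be interpreted. A reader who sees a rate and a Missing count will ask how high the rate could be if the missing patients had done well. That cannot be answered if some of them are already known not to have done well. The same question arises at every time point from 30 days onward.

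**Working it through.** **Step 1. Truth table.** Inputs: the SAP 2.5 conditions and missing clause, reading NO as any condition for YES not met.

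| Perfusion | Thrombosis | SAP code | Logically |
|---|---|---|---|
| pass | pass | YES | YES |
| pass | fail | NO | NO |
| fail | pass | NO | NO |
| fail | fail | NO | NO |
| fail | unknown | missing | **failure** |
| unknown | fail | missing | **failure** |
| pass | unknown | missing | undetermined |
| unknown | pass | missing | undetermined |
| unknown | unknown | missing | undetermined |

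Two of the five missing cells are certain failures. The tick boxes add a third kind: perfusion passing, deployment and proximal-tear boxes both ticked, thrombosis unknown. With the boxes there are 3 × 4 × 3 = 36 patterns. Six are incoherent (perfusion unknown with proximal-tear perfusion ticked), leaving 30: 3 YES, 13 NO, 14 missing. Of those 14, 4 + 1 + 2 = 7 contain a known failure. These are counts of patterns, not of patients.

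**Step 2. Effect on the table.** Let S be successes and C all patients among complete cases, D documented failures with an unknown component, U undetermined patients, and N = C + D + U.

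- Printed rate: S/C.
- Bounds from a single Missing count: S/N to (S + D + U)/N.
- Bounds with D split out: S/N to (S + U)/N.
- Difference: D/N off the upper bound, or 1/N per documented failure. For assumed N of 40, 60 or 80 this is 2.5, 1.7 or 1.25 points.
- S/C exceeds the split upper bound only if D/(D + U) > 1 − S/C.

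**Step 3. Illustration.** The documents give neither the number of dissection patients nor how often a component is unknown, so all inputs here are assumed. Take N = 60 imaged patients: 40 true successes (66.7%) and 20 failures, of which 14 fail one component and 6 fail both. Each component is unknown with probability q. In case (a), S = 40(1−q)², C = 60(1−q)², D = 14q(1−q) + 6·2q(1−q) = 26q(1−q), and U = 40 − S + 14q + 6q². At q = 10%:

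| Unknowns | S | C | D | U | S/C | Lower | Upper, one Missing count | Upper, split |
|---|---|---|---|---|---|---|---|---|
| (a) random, components independent | 32.40 | 48.60 | 2.34 | 9.06 | 66.7% | 54.0% | 73.0% | 69.1% |
| (b) random, both unknown together | 36 | 54 | 0 | 6 | 66.7% | 60.0% | 70.0% | 70.0% |
| (c) only among successes | 32.40 | 52.40 | 0 | 7.60 | 61.8% | 54.0% | 66.7% | 66.7% |
| (d) only among failures | 40 | 56.20 | 2.34 | 1.46 | 71.2% | 66.7% | 73.0% | 69.1% |

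For q = 5% / 10% / 20%:

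- (a) The split removes D/N = 2.1 / 3.9 / 6.9 points. D/(D + U) is 21.1% / 20.5% / 19.3%, below the 33.3% needed for the printed rate to pass the upper bound.
- (c) The printed rate is 64.3% / 61.8% / 56.1%, too low.
- (d) The printed rate is 68.9% / 71.2% / 75.8%, above the split upper bounds of 67.9% / 69.1% / 71.7%.

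**Step 4. Recoding known failures alone.** In case (a), S/(C + D) = 65.2% / 63.6% / 60.2% against a true 66.7%. Moving known failures into NO while partly known successes stay missing biases the rate downward.

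**Step 5. Choice of N.** Suppose 15 of the 60 are dead or have exited (assumed) and case (a) at q = 10% applies to the other 45. If those 15 are counted as undetermined, S = 30 × 0.81 = 24.3, U = 0.75 × 9.06 + 15 = 21.8 and D = 0.75 × 2.34 = 1.76. The bounds are then 40.5–76.8% with the split and 40.5–79.8% without it. On the 45 imaged patients they are 54.0–69.1%. Bounds are informative only on the imaged denominator.

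**The case against.** The strongest reply is that little follows from the coding rule. Complete-case analysis is legitimate, and it is neutral when unknowns are random. Protocol 5.1 allows lighter tests after a clean previous examination, which would tend to make previously clean patients unknown. That is case (c), where there are no documented failures to split out. Both components are imaging findings, so one absent or unsuitable examination may leave both unknown, as in case (b), again with no gain. The endpoint is secondary and untested, and the components are due to appear in Tables 40 and 42 and Listings 18, 20 and 23.

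Most of this stands, and it keeps the point small. Two things remain. The rule as written classes known failures as missing, which is more than an absence of detail. And recovering those patients is laborious: judged by their titles, Tables 40 and 42 do not cross perfusion with thrombosis, so listings would have to be matched patient by patient.

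A reader might infer that Table 51 overstates success. The documents do not support that. It requires failures to be unknown more often than successes, as in case (d), and neither document suggests so. A reader might also infer that the aneurysm and ulcer criteria share the error. They do not carry the unknown-means-missing clause; the SAP is merely silent on partly known composites there.

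**Conclusion.** The point holds in a limited form. Read literally, SAP 2.5 sends three kinds of documented failure to missing: type Ia, Ib or III perfusion ticked with thrombosis unknown; both boxes ticked with thrombosis unknown; and thrombosis known to be incomplete with perfusion unknown. They leave Table 51's denominator and merge with undetermined patients in one row. Table 49 is affected only if it is built from the same variable. The mixing is confined to the Missing row, and no bias in the printed rate is shown.

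The number of patients involved cannot be derived and may be zero. The 2.1 to 6.9 points in case (a) rest on assumed counts and on components going unknown independently. The truth table and the 1/N effect do not depend on those assumptions. Low severity.

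**What to change.** - Define the denominator as dissection patients alive, in the study and imaged at the time point. Count dead, exited and unimaged patients separately.
- Within it, code YES (all components known and passing), NO (any known component fails, taking precedence over unknown) or UNDETERMINED (no known failure, at least one component unknown). Report all three counts.
- Keep the complete-case rate and print beside it the bounds S/N and (S + U)/N. Label them as bounds for missing data, not confidence limits.
- Do not report the known-failure recoding as the only rate.
- State the same precedence for the two-component aneurysm and ulcer criteria, so that Table 49 pools consistently coded components. This is for consistency and does not correct a shown error. The rupture-site criterion has one component and needs no change.

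Cost: some SAP wording and code, including an imaged-at-visit flag, and a few extra rows in Tables 49 to 52. No new data are needed. The downside is longer tables for a secondary descriptive endpoint.

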3 PATIENT SELECTION

3.1 Enrollment criteria

- Any patient with a GORE® TAG® or Conformable GORE® TAG® Thoracic Endoprostheses implant (successful or otherwise) for the treatment of a descending thoracic aortic disease.
- Patients who have previously consented to the collection and use of their personal medical information.
- **18 years or older at the time of treatment.**

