5.4 End of patient participation

5.4.1 Procedure to withdraw from the study

The withdrawal procedure from the study applies when patient data are no longer collected. Discontinuation of patient data collection will occur in the following cases:

- The patient decides to withdraw from the study at any time, for whatever reason, without having to justify such a decision
- Decision made by the doctor to stop the patient's participation in the study in order to protect the patient's well-being
- Patient lost to follow-up
 - Note: the patient may not be considered as being lost to follow-up by the investigator as long as the follow-up period (5 years) has not elapsed.
- Patient's death
- Normal end of the observational study

Data on patients, for whom the study endoprosthesis was introduced at the arterial access but not inserted during the initial intervention (failed installation), will be collected until the patient's withdrawal. Thereafter, a withdrawal form from the observational study must be completed.

Patients for whom the endoprosthesis will be explanted during the follow-up period should be evaluated clinically at least until the last 5-year visit.

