### 2.3. Analysis Sets

#### 2.3.1. Definition of patient populations

2 populations will be defined:

- The “included” population will include all patients enrolled in the study.
- The Per Protocol (PP) population will include all “included” patients for whom the GORE® TAG® and Conformable GORE® TAG® thoracic endoprosthesis were introduced through surgical or percutaneous approach, and who fulfill the eligibility criteria.

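### The SAP rules for exclusion of the aneurysm, ulcer and rupture site do not require an endoprosthesis to be in place, so an assessed patient without a device can score as excluded

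*SAP*

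**What the plan says.** **The rules.** SAP 2.5 derives exclusion separately for each lesion type:

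- Aneurysm: "No maximum diameter of the aneurysm sac increase > 5 mm (compared to 1 st post-op exam) and no type I or type III endoleak".
- Penetrating ulcer: "No maximum aortic diameter of the ulcer increase > 5 mm" relative to the first post-operative examination, again with no type I or III endoleak.
- Rupture site: after "Derived criterion 'exclusion of the rupture site without endoleak' will be defined as follows", the only condition is the absence of a type I or III endoleak.
- False lumen: this rule needs positive evidence of complete thrombosis, and it sets the result to missing when perfusion or thrombosis status is unknown.

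The definitions in Protocol 2.2.2 likewise set no device-in-place condition for the first three.

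**The patients.** Protocol 3.1 enrols any patient with an "implant (successful or otherwise) for the treatment of a descending thoracic aortic disease". SAP 2.3.1 places in the per-protocol (PP) set those whose "thoracic endoprosthesis were introduced through surgical or percutaneous approach, and who fulfill the eligibility criteria", and SAP 2.4 runs all analyses on that set. Protocol 5.4.1 recognises patients "for whom the study endoprosthesis was introduced at the arterial access but not inserted during the initial intervention (failed installation"). Their data are collected until withdrawal, and a withdrawal form follows. The same section asks for clinical evaluation of explanted patients up to the 5-year visit.

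**Timing and missing data.** SAP 2.4.3.2 reports the exclusion rate from 30 days onward. SAP 2.1.3 replaces no missing data and treats a patient who stops early as missing from the last follow-up. SAP 2.1.1 bases percentages on non-missing observations.

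**The concern.** In their usual meaning, which the documents do not spell out, type I and type III endoleaks are leaks at or through an implanted endoprosthesis. A patient with no endoprosthesis cannot have one. Three of the four rules therefore treat the absence of a device in the same way as the absence of a leak, and an untreated lesion can enter the numerator as a success.

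Exclusion is the first-listed secondary endpoint, and it is the one that asks whether the lesion was actually sealed. The affected outputs are the pooled rate (Table 49) and the aneurysm, ulcer and rupture-site rates (Tables 50, 52 and 53). The indication-specific tables rest on fewer patients, so one misclassified patient moves them more.

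**Working it through.** The plan states no exclusion rate and no failed-installation rate, so there is no figure to reproduce. The check has two parts.

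**1. The written rules applied to a patient with no device**

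| Situation | Rupture site | Aneurysm or ulcer |
|---|---|---|
| Assessed, growth not above 5 mm | YES | YES |
| Assessed, growth above 5 mm | YES | NO |
| Left the study before assessment | missing | missing |

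The rupture-site column contains no NO. For aneurysm and ulcer, growth is measured from the first post-operative examination. If that is also the examination used at 30 days, growth is zero by construction and the result is YES.

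The YES rows can be reached: Protocol 5.1 places a post-operative visit with imaging between D1 and D30, and no withdrawal date is fixed for failed installations. A YES could also arise if an unticked endoleak box were programmed as no endoleak, because these three rules have no unknown-status clause.

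**2. Size**

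Let N be the patients assessed, s the true exclusions among implanted patients, and f the assessed non-dissection patients without a device who meet the written rule.

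- As written: (s + f)/N
- Scored NO: s/N
- Difference: f/N, whatever the true exclusion rate

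Assume N = 160 (the planned enrolment, all assessed) and f from 1 to 8:

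- f = 1: 1/160 = 0.6 points
- f = 2: 2/160 = 1.25 points
- f = 4: 4/160 = 2.5 points
- f = 8: 8/160 = 5.0 points

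Worked example with f = 4 and 90% exclusion among the 156 implanted patients (0.90 × 156 = 140.4, taken as 140), with exact 95% intervals:

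- As written: (140 + 4)/160 = 90.0% (84.3 to 94.2)
- The four scored NO: 140/160 = 87.5% (81.4 to 92.2)
- The four missing: 140/156 = 89.7%

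If all four leave before assessment, the error from scoring YES is 0. They still drop out of the denominator, and the rate stays 89.7 − 87.5 = 2.2 points above the one that counts them as failures.

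In an assumed indication group of 20 with one such patient and 17 of 19 implanted patients excluded, the table shows 18/20 = 90.0% (68.3 to 98.8) instead of 17/20 = 85.0% (62.1 to 96.8), a shift of 5 points.

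**The case against.** The strongest reply is that the plan may remove most of these patients before the rule is applied. Data on failed installations stop at withdrawal, later visits are missing, and denominators use non-missing observations only. Protocol 5.1 also imposes no examination outside a centre's usual practice, so some may never be imaged. A reader might infer that every failed installation is counted as a success. The documents do not support that: some or all may be missing, and the final eCRF, which would show how endoleak fields are completed for a patient without a device, is not available. This part of the reply stands. It limits the size of the problem but does not correct the rule, since missing also keeps a known failure out of the rate.

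A reader might also infer a pooled bias of 2 to 5 points by applying a 2% to 5% failure rate to all 160 patients. That is not supported either. The failure rate has no basis in the documents, and dissections are scored by a different rule. If 40% of patients had dissections (an assumption) with the same failure rate, the shift would be 0.6 × 2% = 1.2 to 0.6 × 5% = 3 points, before removing patients with no assessment.

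Nor is it certain that a dissection patient without a device scores NO. The false-lumen rule refers to the treated part of the aorta; without a device there is none, and an unknown status gives missing.

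Finally, the endpoint is descriptive, with no test or success threshold in the visible text, and deployment failures are disclosed in Table 31 and Listing 13. That limits the consequence. However, a reader of Tables 49 to 53 would not see that such patients sit in the numerator.

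**Conclusion.** The point holds as a defect in three derivation rules. An assessed patient without a device scores YES for rupture site always, and for aneurysm or ulcer unless growth exceeds 5 mm. A patient who leaves first is missing. Any resulting error favours the device.

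The size cannot be determined from the documents. Scoring YES instead of NO shifts the rate by the number of assessed non-dissection patients without a device, divided by the number assessed: 0 if all leave first, 0.6 points for 1 of 160, 5 points for 8 of 160, and 5 points for one patient in a group of 20. All these counts are assumptions.

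For failed installations the effect is probably confined to the early time point. Explanted patients extend it to later visits if they are imaged, which Protocol 5.4.1 does not state, since it mentions clinical evaluation only. The change is worth making because a stated rule gives a wrong result and the correction is cheap.

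**What to change.** In SAP 2.5, with Protocol 2.2.2 aligned, for the aneurysm, ulcer and rupture-site criteria:

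- Allow YES at a visit only if a study endoprosthesis is deployed and in place at that visit and the endoleak status is known.
- Score a failed installation with no study endoprosthesis in place as NO at the 30-day time point. This does not replace a missing value, because the failure is known from the deployment field. Tie the rule to the visit rather than to the index procedure, so that a later successful repair is not locked at NO.
- Leave visits after study exit missing, as SAP 2.1.3 states.
- Do not score explanted patients YES because no endoleak is recorded. State whether they count as not excluded or not evaluable.
- Set unknown endoleak status to missing, as the false-lumen rule already does for its own inputs.
- Footnote the number of patients without a device at each time point in Tables 49 to 53.

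Deployment success is already tabulated (Table 31). The sponsor should confirm that the eCRF also identifies explantation. The cost is a small wording change in both documents, a few program conditions and a slightly less favourable reported exclusion rate.
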